8.4.2 Body Mass Index (BMI)

BMI is the subject's body weight in kilograms divided by the square of the subject's height in meters.

 $BMI = weight in kilograms / (height in meters)^2$

8.4.3 Mullen Developmental Age (DA) and Developmental Quotient (DQ)

Mullen Developmental Age (in months) is calculated as the mean of the age equivalents obtained from the scores of four out of the five domains of the scale except Gross motor.

Mullen DA = (Fine Motor Age Eq + Receptive Language Age Eq + Expressive Language Age Eq + Visual Reception Age Eq) / 4

Mullen DQ = (Mullen DA / Chronological Age) * 100

8.4.4 Vineland Adaptive Age Equivalent and Adaptive Developmental Quotient (DQ)

Vineland Adaptive Developmental (in months) is calculated using the Age Equivalents from the 11 subdomains of the scale. Instead of using the mean of the 11 subdomains, the subdomains are first grouped into four areas, and the Adaptive Age Equivalent is calculated from the mean of those four areas. Example:

- Communication Age Equivalent is calculated as the mean of: Receptive Age Eq + Expressive Age Eq + Written Age Eq
- Daily living skills Age Equivalent is calculated as the mean of: Personal Age Eq + Domestic Age Eq + Community Age Eq
- Socialization Age Eq is calculated as the mean of: Interpersonal relationships Age Eq + Play and Leisure Time Age Eq + Copying Skills Age Eq
- Motor Skills Age Eq is calculated as the mean of: Fine Age Eq

Vineland Adaptive Age Equivalent = (Communication Age Eq + Daily living skills Age Eq + Socialization Age Eq + Motor Skills Age Eq) / 4

Vineland DQ = (Vineland Age equivalent / Chronological Age) * 100

The Vineland Adaptive AE and Adaptive DQ scores will be collected through Case Report Forms (CRF) and will not be recalculated during programming.

8.4.5 Cognitive Bayley Developmental Age (DA) and Cognitive Developmental Quotient (DQ)

Mean Developmental Age (DA) = (Developmental Age for Cognitive + Developmental Age for Receptive Language + Developmental Age for Expressive Language + Developmental Age for Fine Motor) / 4

Cognitive DQ = (Cognitive Developmental Age / Chronological age) *100

| 8.4.6 | CCI |
|-------|-----|
| | |
| | |
| | |
| | |
| ٠ | CCI |
| ٠ | |
| • | |
| • | |
| • | |
| • | |
| | |
| CCI | |

DQ = (Mean Developmental Age/ Chronological age) *100

8.4.7 Modified Children's Sleep Habits Questionnaire (CSHQ)

CSHQ total score is calculated by adding all the 8 subscores. All scores will be collected through CRF and will not be recalculated during programming.

8.4.8 Pediatric Quality of Life Inventory (PedsQLTM)

The PedsQL Core Generic Scales will use PedsQL Core Total Score in CRF. The PedsQL Gastrointestinal Symptoms Scales will use PedsQL GI Symptoms Score in CRF.

8.4.9 Parenting Stress Index, 4th Edition (PSI-4)

Total raw score is calculated by adding the three subscores: Raw score = (PD) + (P-CDI) + (DC). The raw score will be converted to total stress score. All scores will be collected through CRF and will not be recalculated during programming.

8.4.10 Parent Global Impression Score (PGI)

PGI total score is calculated by adding all the 9 subscores. All scores will be collected through CRF and will not be recalculated during programming.

8.4.11 Clinical Global Impression Improvement (CGI)

The Clinical Global Impression Improvement Scale Score will use CGI Global Improvement score in CRF.

8.4.12 Parent Symptoms Score Questionnaire (PSSQ)

The Parent Symptoms Score Questionnaire contains 29 symptoms with an indicator of whether the symptom was present or absent, and if present, a ranking value. Number of patients who have the symptom and average rank for each symptom will be calculated by visit.

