- Bayley Scales of Infant and Toddler Development – Version III - Cognitive, Language and Motor. If children obtain a developmental age older than 36 months with the Bayley, the Kaufman Assessment Battery for Children, Second Edition, will be used also and will replace the Bayley Scales in the next visits
- Pediatric Quality of Life Inventory (PedsQL™) Core Generic Scales for parents
- Pediatric Quality of Life Inventory PedsQL™ Gastrointestinal Symptoms Scales for parents

The neurocognitive evaluations at this visit and along all other visits during the study will be CCI to allow for the possibility of future auditing by an external psychologist.

The Vineland Adaptive Behaviour scale will always be the first cognitive/adaptive functioning scale to be used in all visits, to obtain an estimate of the child's developmental level that will help for following evaluations.

The KABC-II subtests required for the Fluid-Crystalized Index (FCI) will be administered. After the FCI is completed, the subtests required for the Nonverbal Index will be administered if the child is able to continue with the testing session.

The rater/s and parent participating on the evaluation should be consistently the same during the trial for each participant as much as possible. These assessments may be performed locally with an external rater, if the family signed the consent annex and there is a qualified rater trained for the study procedures.

- Modified Children's Sleep Habits Questionnaire (CSHQ)
- Parent Symptom Score Questionnaire, to collect list of symptoms and associated ranking.

Vector shedding samples for urine, feces and saliva are collected at Screening Visit 1. In the event that urine, saliva and/or feces samples are unable to be obtained at Screening Visit 1, they will be obtained at Screening Visit 2.

The following evaluations will be conducted during Screening Visit 2:

- Weight
 - The weight obtained at Screening Visit 2 will be used to calculate the viral vector dose
- Adverse events
- Concomitant medications

- CCI [REDACTED]
- Cognitive function and adaptive functioning assessment using:
 - Neurocognitive validity form (final set up for following scales)
 - Mullen Scales of Early Learning, both non-verbal assessments of cognitive function. If children obtain a developmental age older than 60 months with the Mullen, the Kaufman Assessment Battery for Children, Second Edition, will be used also and will replace the Mullen Scales in the next visits

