4.2 Secondary Endpoints

- Change from baseline in plasma or urine glycosaminoglycans or heparan sulfate after treatment at Month 1, 6, 12
- Change from baseline in CSF or plasma or leukocyte SGSH enzyme activity levels after treatment at Month 1, 6, 12
- Change from baseline in brain volumes after treatment, as measured by MRI at Month 12
- Change from baseline in sleep pattern as measured by the modified Children's Sleep Habits Questionnaire (CSHQ) at Month 6, 12
- Change from baseline in Pediatric Quality of Life Inventory (PedsQL[™]) Core Generic Scales total score at Month 6, 12
- Change from baseline in parent quality of life, using the Parenting Stress Index, 4th Edition (PSI-4) at Month 6, 12
- Change from baseline in gastrointestinal symptoms using the PedsQLTM Gastrointestinal Symptoms Scales at Month 6, 12
- Parent Global Impression Score at Month 6, 12
- Clinical Global Impression Improvement Scale at Month 6, 12
- Change from baseline in Parent Symptoms Score Questionnaire at Month 6, 12
- Change from baseline in Body Mass Index (BMI) after treatment at Month 6, 12
- Incidence and change from baseline in abnormalities in standard awake 45-minutes-EEG monitoring at Month 6, 12
- Determination of vector shedding analysis in plasma, saliva, urine and feces will provide preliminary data for the Environmental Risk Assessment (ERA)

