5.1 Intent-to-Treat Set (ITT)

The ITT Set will include all enrolled subjects who received ABO-102 and have at least one post-baseline efficacy measurement. Efficacy and safety analyses will be conducted based on the ITT Population.

The primary endpoints, secondary endpoints, **CCI** endpoints will be analyzed using the ITT Set. At the time of the study termination, all 5 enrolled subjects were treated and had at least one post-baseline assessment. Therefore, the ITT Population is equivalent to all patients enrolled and will be used to evaluate both safety and efficacy data and for populating listings.

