8.1.4 Handling of Missing or Partial Data

- Missing baseline values will not be imputed in any situation.
- Missing post-baseline values for by-visit data will be summarized using the protocoldefined visit windows. If a value is not available within a given window, no imputation will be done.
- If day of birth is missing, the 1st day of the month will be used to calculate chronological age.
- Missing data for AE relationship will be imputed as "Related".
- For incomplete dates for AEs or non-study medications, the missing component(s) will be assumed as the most conservative value(s) possible. Actual data values, as they appear in the clinical database, will be shown in the data listings. Rules for partial dates are described in the table below. If the AE year is missing or AE is ongoing, the end date will not be imputed. Note: in the table, D = day, M = month, and Y = year.

| Parameter | Missing | Additional Conditions | Imputation |
|--------------------|------------|-----------------------------------|----------------------------------|
| Start date for AEs | Time only | | Time will not be imputed; but |
| | | | will be assumed to be after gene |
| | | | transfer time |
| | D only | M and Y same as M and Y of gene | Date of gene transfer |
| | | transfer date | |
| | | M and/or Y not same as M and Y | First day of non-missing month |
| | | of gene transfer date | |
| | D and M | Y same as Y of gene transfer date | Date of gene transfer |
| | | Y not same as Y of gene transfer | Use January 1 of non-missing |
| | | date | year |
| | M, D and Y | None – date completely missing | Date of gene transfer |
| Stop date for AEs | Time only | | Time will not be imputed |
| | D only | | Last day of non-missing month |
| | D and M | | Use December 31 of non- |
| | | | missing year |
| | M, D and Y | Deceased | Date of death |

| Parameter | Missing | Additional Conditions | Imputation |
|------------------|------------|-----------------------------------|--------------------------------|
| | | Not deceased | Date of the end of trial |
| | | | participation |
| Start date for | D only | M and Y same as M and Y of gene | Date of gene transfer |
| concomitant meds | | transfer date | |
| | | M and/or Y not same as M and Y | First day of non-missing month |
| | | of gene transfer date | |
| | D and M | Y same as Y of gene transfer date | Date of gene transfer |
| | | Y not same as Y of gene transfer | Use January 1 of non-missing |
| | | date | year |

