8.2.2 Analyses of Secondary Efficacy Endpoints

- Change from baseline in plasma or urine glycosaminoglycans or heparan sulfate after treatment at Month 1, 6, 12
- Change from baseline in CSF or plasma or leukocyte SGSH enzyme activity levels after treatment at Month 1, 6, 12
- Change from baseline in brain volumes after treatment, as measured by MRI at Month 12
- Change from baseline in sleep pattern as measured by the modified CSHQ at Month 6, 12
- Change from baseline in PedsQLTM Core Generic Scales total score at Month 6, 12
- Change from baseline in parent quality of life, using the PSI-4 at Month 6, 12

[figure not shown]
- Change from baseline in gastrointestinal symptoms using the PedsQL[™] Gastrointestinal Symptoms Scales at Month 6, 12
- Change from baseline in Parent Symptoms Score Questionnaire at Month 6, 12
- Parent Symptoms Score Questionnaire at Month 6, 12
- Parent Global Impression Score at Month 6, 12
- Clinical Global Impression Improvement Scale at Month 6, 12
- Incidence and change from baseline in abnormalities in standard awake 45-minutes-EEG monitoring at Month 6, 12

All of the above secondary efficacy endpoints will be presented by listings only.

• Determination of vector shedding analysis in plasma, saliva, urine and feces will provide preliminary data for the ERA

Vector shedding samples will continue to be collected and analyzed until two consecutive negative samples are collected or completion of the study by the subject, whichever comes first.

Observed values and change from baseline in copies per 1mL of specimen in plasma, saliva, urine and feces will be summarized descriptively at baseline and each post-baseline time point. Copies per 1mL of specimen in feces will be presented as a spaghetti plot over each visit by subject.

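### The SAP assigns the Parent Symptoms Score Questionnaire to listings in 8.2.2 but to by-visit averages in 8.4.12, and the average rank compares different children across visits instead of measuring change from baseline

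*SAP*

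**What the plan says.** - **Endpoint.** SAP 4.2 defines it as "Change from baseline in Parent Symptoms Score Questionnaire at Month 6, 12". Protocol 5.7 also defines it as a change from baseline.
- **Presentation.** SAP 8.2.2 lists the PSSQ twice, once as change from baseline and once without the change. It closes the list with "All of the above secondary efficacy endpoints will be presented by listings only". Vector shedding, which comes after that sentence, is the only endpoint in the section given a descriptive summary.
- **Derivation.** SAP 8.4.12 says the questionnaire "contains 29 symptoms with an indicator of whether the symptom was present or absent, and if present, a ranking value", and continues: "Number of patients who have the symptom and average rank for each symptom will be calculated by visit".
- **Instrument.** Protocol 5.3.1 describes it only as "Parent Symptom Score Questionnaire, to collect list of symptoms and associated ranking".
- **Missing values.** SAP 8.1.4 says of post-baseline data: "If a value is not available within a given window, no imputation will be done".
- **Numbers.** SAP 5.1 says: "At the time of the study termination, all 5 enrolled subjects were treated and had at least one post-baseline assessment".

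Neither document gives the direction or range of the rank, the denominator of its average, a value for an absent symptom, or a change score for the PSSQ.

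**The concern.** There are two problems.

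**The instructions conflict.** A count of patients and a mean across patients are group summaries. They are not lines in a by-subject listing of the kind SAP 8.1.1 describes. A programmer following 8.2.2 builds no table, and one following 8.4.12 builds one. The sentences concerned are not redacted, and SAP section 10 does not mention the point.

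**The average rank is a weak summary if it is produced.** If only children with the symptom contribute, the contributing group changes between visits. A difference between two visit means then mixes change within children with change in who is counted. The endpoint is change from baseline, which is a within-child quantity, and two visit means over different children do not estimate it.

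At stake is how one secondary table reads. With five children, one or two resolutions can set the apparent direction.

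**Working it through.** The plan states no figure on this point, so there is none to reproduce.

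**Step 1: the two instructions side by side.**

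| SAP section | Unit | Output |
|---|---|---|
| 8.2.2 | Child by visit | Listing alone |
| 8.4.12 | Symptom by visit | Count and mean rank across children |

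The outputs differ in kind, and no sentence in the SAP says which governs.

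**Step 2: behaviour of the average.** Inputs: five children (SAP 5.1), and a rank that exists only when the symptom is present (SAP 8.4.12). Assumptions: ranks run from 1 to 5, and the mean is taken over children with the symptom at that visit. The formula is mean rank = (sum of ranks among children with the symptom) / (number of children with the symptom). Baseline ranks 1, 2, 3, 4, 5 give 15/5 = 3.0. No remaining child changes in the first two cases.

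- *1 is worst; the children ranked 4 and 5 lose the symptom:* (1+2+3)/3 = 2.0. The mean moves toward the worse end.
- *5 is worst; the children ranked 1 and 2 lose the symptom:* (3+4+5)/3 = 4.0. The mean again moves toward the worse end.
- *5 is worst and every child improves:* baseline 1, 1, 1, 5, 5 gives 13/5 = 2.6. Three children lose the symptom and two go from 5 to 4, giving (4+4)/2 = 4.0.
- *1 is worst and every child improves:* baseline 1, 1, 5, 5, 5 gives 17/5 = 3.4. Three children lose the symptom and two go from 1 to 2, giving (2+2)/2 = 2.0.

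**Step 3: is there a systematic direction?** Take every set of five ranks from 1 to 5 and let each child in turn lose the symptom with nothing else changing: 5^5 × 5 = 15,625 cases, weighted equally. The mean moves toward worse in 47.5%, toward better in 47.5%, and not at all in 5.0%. The split is the same for either rank direction. The direction of movement therefore says nothing about the resolution that caused it.

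**Step 4: would scoring an absent symptom as 0 repair it?** Only if higher is worse. The second case in Step 2 then gives (0+0+3+4+5)/5 = 2.4, down from 3.0, which is the right way. If 1 is worst, the first case gives (1+2+3+0+0)/5 = 1.2, which is the wrong way. The rank direction would have to be stated first.

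**Step 5: the within-child alternative on the same data.** In each of the first two cases in Step 2, the shift count is 2 present to absent, 0 absent to present and 3 still present. The paired rank change among the three children with the symptom at both visits is 0, 0, 0. Both summaries report what happened, whichever end of the scale is worst.

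**The case against.** The strongest reply has four parts.

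1. **The patient count is reported beside the average.** In either of the first two examples it falls from 5 to 3, so an attentive reader sees that children lost the symptom. This stands and limits the harm. It does not make the two means comparable.
2. **The denominator is inferred.** The SAP does not say outright that only children with the symptom are averaged. This also stands. It is the natural reading, since no rank exists otherwise, nothing is imputed and no value is set for an absent symptom.
3. **The two complaints do not add up.** If 8.2.2 governs, the average is never shown and does no harm. That is correct: the second problem bites only if 8.4.12 prevails. The conflict has to be settled in either case.
4. **Five children can be read from the listing.** SAP 8.1 puts all collected data in listings, and no test is planned for this endpoint. This keeps the point minor.

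A reader might infer two stronger claims that the documents do not support.

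- *When one symptom resolves, the child's other symptoms move up in rank.* That holds only if ranks are an ordering within each child. Neither document says so. The value could be a separate rating for each symptom.
- *The average is biased toward showing worsening.* Step 3 of the working shows an even split. The examples show what can happen, not what will usually happen.

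**Conclusion.** The point holds in a limited form. SAP 8.2.2 and 8.4.12 give instructions that cannot both be followed, and this rests on the text alone. On the plain reading, the by-visit average rank compares different children across visits and can move in either direction when a symptom resolves. In the examples a mean of 3.0 goes to 2.0 or to 4.0, looking like deterioration when the only change is that two children lost the symptom. The sizes depend on the assumed 1 to 5 range. That resolution alone can move the mean either way does not depend on that range or on which end is worst, but it does depend on averaging over present cases only. The statistic also does not measure the stated change-from-baseline endpoint.

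Severity is low: a secondary, descriptive endpoint in five children, with the patient count alongside. It is a desirable correction, and no primary conclusion depends on it.

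**What to change.** - **SAP 8.2.2:** exempt the PSSQ from the listings-only sentence, and remove the duplicate PSSQ entry so that change from baseline is the single stated endpoint.
- **SAP 8.4.12:** replace the by-visit average rank with within-child shift counts from baseline for each of the 29 symptoms (present to absent, absent to present) at Months 6 and 12.
- **Ranks:** keep individual ranks in the listing. If they are summarised at all, use only the paired change among children who have the symptom at both visits, give the number of pairs, and state the rank's direction and range.

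The cost is a few lines of SAP wording and one small table from data already collected. The small downside is that shift counts do not capture change in the severity of a symptom that persists. The listed ranks, or the optional paired change, cover that as far as the rank reflects severity.

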9 STATISTICAL SOFTWARE

All statistical analyses will be performed using SAS® version 9.4.

10 CHANGES FROM THE PROTOCOL

Due to the study early termination and only 5 subjects being enrolled, there will be no comparison to natural history study data.
